### **3. 3 Enrollment of all Minority groups and Females**

The eltrombopag treatment will be offered to both genders and all racial and ethnic groups who meet the eligibility criteria of this clinical study.

## **4.0 STUDY DESIGN**

### **4.1 Overall Design**

This is a single institution, single arm, non-randomized phase II clinical trial with a sample size of 31 patients. The primary goal of this trial is to determine if eltrombopag can accelerate platelet count recovery in older AML patients (age  $\geq$ 60 years) who have no morphological evidence of leukemia in the bone marrow following remission IC. The standard remission IC for AML in patients  $\geq$ 60 years will consist of an anthracycline (daunorubicin or idarubicin) for 3 days and cytarabine as continuous intravenous infusion for 7 days. The patients in the study will receive supportive blood transfusions as part of standard of care at the Cleveland Clinic. Use of erythropoiesis stimulating agents (ESA) or granulocyte colony stimulating factors (G-CSF) during or following remission IC is not permitted. The study schema is shown below.

In those patients who have no morphologic evidence of disease on day 14 (range, 14-17) bone marrow evaluation, eltrombopag will be administered within 5 business days from the date of day 14 (range, 14-17) bone marrow biopsy. There will be a gap of at least one week (range, 7-9 days) between the last day of remission IC and initiation of eltrombopag, which will allow sufficient time for complete washout of the chemotherapeutic agents. Dose modification will be determined based on platelet counts and presence of adverse event(s).

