### **3.0 SELECTION OF PATIENTS**

#### **3.1 Inclusion Criteria**

1. Patients must be  $\geq$  60 years of age.
2. All categories of AML will be included except for acute promyelocytic leukemia (APL) [AML-M3 as defined by 1976 French-American-British (FAB) classification, or APL with t(15;17)(q22;q12); *PML-RARA* as defined by the revised 2008 World Health Organization (WHO) classification of myeloid neoplasms and acute leukemias], acute megakaryocytic leukemia [AML-M7 type as per FAB or AML (megakaryoblastic) with t(1;22)(p13;q13); *RBM15-MKL1* as per WHO 2008 revised classification] and acute leukemias of ambiguous lineage (as per WHO 2008 revised classification)], undergoing 7 + 3 remission IC with cytarabine and an anthracycline (daunorubicin or idarubicin). All cases have to be histopathologically confirmed by a diagnostic bone marrow biopsy. Use of granulocyte colony-stimulating factor (G-CSF) for any indication must have been discontinued at least 7 days prior to entry into the study.
3. Patients with secondary AML arising out of MDS (all subtypes under WHO classification), chronic myelomonocytic leukemia (CMML); therapy-related AML and those with a prior autologous hematopoietic cell transplantation are eligible.
4. No morphological evidence of disease (defined as marrow myeloblast percentage of < 5% and/or documentation from hematopathologist indicating no morphological evidence of leukemia) on day 14 bone marrow examination (range, day 14-17; day 1 refers to the first day of IC) following remission IC.
5. Must be able to give voluntary informed written consent to participate in the study. Informed consent will be obtained prior to starting remission IC (can be obtained even on the first day of remission IC if obtained before administration of chemotherapy) and before any study-related procedure not part of normal medical care, with the understanding that consent may be withdrawn by the subject at any time without prejudice to future medical care.
6. Women of childbearing potential should be advised to avoid becoming pregnant and men should be advised to not father a child while receiving treatment. All men and women of childbearing potential must use acceptable methods of birth control throughout the study as described below:

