### **8.4 Long-term Follow-up**

All participants, regardless of reason for discontinuation, will be followed for survival and for AML transformation (an increase of blasts to a level  $\geq 20\%$  in peripheral blood or bone marrow) for five years from study registration as part of standard of care for CCF leukemia patients.

The following study calendar will be used:

	Pre- induction	Week 1	Week 2	Week 3	Week 4	Week 5	Week 6
						Inpatient/Outpatient	
Induction chemotherapy (IC)							
Study Medicationa							
Informed Consent	X						
Demographicsb	X						
Disease Characteristicsc	X						
Transfusion Historyd	X	X	X	X	X	X	X
Review of concurrent medications	X	X	X	X	X	X	X
Physical Examinatione	X	X	X	X	X	X	X
CSBEf	X	X	X	X	X	X	X
Performance statusg	X						
Hematologyh	X	X	X	X	X	X	X
Serum Biochemistryi	X	X	X	X	X	X	X
Chest x-ray	X						
Peripheral Blood Smearj	X					X	
Bone marrow biopsyk	X		D14 - 17			X	
Ophthalmology examl	X						
12 lead ECG	X			X m			
Adverse event monitoringn				X	X	X	X

Pre-induction assessment refers to evaluation at the time of diagnosis of AML prior to start of remission induction chemotherapy. Weeks as enumerated in the table refer to the time from the start date (day 1) of remission induction chemotherapy.

Week 1 is the week when the patient receives the standard 7+ 3 (cytarabine and anthracycline) remission induction chemotherapy

a. **Study Medication:** Eltrombopag dose as assigned. The drug will be started within 5 business days from the date of day 14 bone marrow biopsy if the day 14 bone marrow biopsy (range, 14-17) shows no morphological evidence of leukemia and will be continued for a total of 4 weeks unless discontinued earlier for reasons stated in the protocol.

b. **Demographics:** Date of birth, race, ethnicity, and gender.

c. **Disease Characteristics:** Date of AML diagnosis, AML category as classified by WHO, primary vs. secondary AML, type of secondary AML (antecedent hematologic disorder, therapy-related including prior radiation therapy and or cytotoxic chemotherapy for any condition).

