d. **Transfusion History:** Transfusion requirements of red blood cells and platelets up to 8 weeks prior to the diagnosis of AML and during hospital stay.

e. **Physical Examination:** Weight, height (during screening only), body temperature (oral), blood pressure, pulse rate, respiratory rate and pulse oximetry (oxygen saturation).

f. **CSBE:** Clinically Significant Bleeding Events includes hematuria, gastrointestinal bleed, retroperitoneal bleeding, intra-cranial bleed, epistaxis not controlled by conservative measures and muscle or soft tissue hematomas. CSBE will not include petechial skin rash, ecchymosis or mucosal petechiae.

g. **Performance Status** as per ECOG scale.

h. **Hematology:** CBC with differential will be monitored daily during hospital stay. Once the patient is discharged, CBC with differential will be checked within 72 hours, thereafter CBC with differential will be checked weekly until the subject's platelets reach 100,000/ $\mu$ L. Once the platelet counts reach 100,000/ $\mu$ L, the labs will be done at the discretion of treating physician as part of routine standard of care.

i. **Serum Biochemistry:** Complete metabolic panel (CMP) will be checked daily during hospital stay. CMP will include albumin, total protein, alkaline phosphatase, total bilirubin, SGOT[AST], SGPT[ALT], sodium, potassium, chloride, bicarbonate, BUN, creatinine, glucose, and calcium. Magnesium and phosphorus will be resulted if clinically indicated. Once the patient is discharged, CMP will be checked weekly until the subject's platelets reach 100,000/ $\mu$ L. Once the platelet counts reach 100,000/ $\mu$ L, the labs will be done at the discretion of treating physician as part of routine standard of care. ELISA for HIV and remote hepatitis panel will be checked only once at the time of study screening (pre-induction).

j. **Peripheral Blood Smear:** Will be performed prior to start of induction chemotherapy, typically between day 30 and 45 of induction chemotherapy while checking for remission status, and at the end of the study period (optional) based on clinical assessment.

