## 10.0 STUDY ENDPOINTS

### 10.1.1 Primary endpoint

The proportion of patients achieving a platelet count of  $\geq 50,000/\mu\text{L}$  by day 24 of IC on eltrombopag therapy. The treatment response parameters for platelet count recovery for this trial was derived from a cohort of 200 older AML patients (excluding acute promyelocytic leukemia and acute megakaryocytic leukemia) who underwent aggressive 7 + 3 cytarabine-based remission IC at the Cleveland Clinic between 2000 and 2011. The total CR rate in our historical cohort was 41%.

The median time to CR (defined as the time from the start date of IC to the achieving CR per

IWG criteria) was 34 days (range, 14-66). The median time to reach platelet counts  $> 50,000/\mu\text{L}$  was 24 days (range, 17-57) from the start date of IC.

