## 10.2. Secondary endpoints

**1) Kinetics of megakaryocyte recovery:** Parameters to be assessed will include median time to reach platelet count  $\geq 50,000/\mu\text{L}$  and  $\geq 100,000/\mu\text{L}$ , number of days of platelet transfusion, rates of platelet transfusion-independence, median time to reach platelet transfusion-independence and rates of CSBE. The initial time point for assessing different platelet recovery periods will be the first day of remission IC. The number of days of platelet transfusion will be defined as the total number of days in the cycle, beginning with the first day of study drug administration, in which a patient received transfusion. The time to transfusion-independent platelet recovery will be defined as the number of days from the first day of IC until the first of the 5 consecutive days with platelet count equal to or greater than  $50,000/\mu\text{L}$  without a platelet transfusion. For patients who do not achieve platelet recovery before the end of the study, the time to platelet recovery will be censored on the last day of the study. CSBE refers to all bleeding events that require intervention including, but not limited to, transfusional support (red blood cells, platelets and other blood products such as fresh frozen plasma or cryoprecipitate). CSBE will include hematuria, gastrointestinal bleed, retroperitoneal bleed, intra-cranial bleed, uncontrolled epistaxis and muscle or soft tissue hematomas.

**2) Kinetics of granulocytic recovery:** Parameters to be assessed will include the median time to reach absolute neutrophil count (ANC) equal to or greater than  $500/\mu\text{L}$  (first of the five consecutive days with ANC  $\geq 500/\mu\text{L}$ ) and the median time to reach ANC equal to or greater than  $1000/\mu\text{L}$  (first of the five consecutive days with ANC  $\geq 1000/\mu\text{L}$ ) counted from the first day of study drug administration. A neutrophil response will be defined as an absolute increase in ANC of more than  $1000/\mu\text{L}$  within 4 weeks of remission IC.

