## 12.0 STATISTICAL CONSIDERATIONS

The primary goals of this trial are to assess the efficacy and safety of a short course of eltrombopag in elderly AML patients who have no morphological evidence of residual disease on bone marrow biopsy following standard 7+3 induction therapy. The primary endpoint is the proportion of patients with early (by day 24 from the start of induction) platelet recovery to  $\geq 50,000/\mu\text{L}$ . Based on historical data and our own institutional data (unpublished) approximately 60% of patients can be expected to recover platelets to  $\geq 50,000/\mu\text{L}$  by day 24 without additional supportive care beyond platelet transfusions. An increase in the recovery rate to  $\geq 80\%$  would be considered indicative that eltrombopag has significant efficacy in this population.

A two-stage accrual design with a maximum accrual goal of 31 eligible and evaluable patients will be used to test this hypothesis. Twelve eligible patients will be studied initially. If eight or more (67%) have full platelet recovery by day 24 an additional 19 eligible patients will be assessed. If overall 21 or more of the 31 patients have platelet recovery (observed recovery rate  $\geq 68\%$ ) eltrombopag will be accepted for further testing. With this design, there is a  $\geq 56\%$  likelihood of stopping early if eltrombopag's true recovery rate is  $\leq 60\%$ , whereas there is at most a 7% chance if the true recovery rate is  $\geq 80\%$ . The overall likelihood of rejecting eltrombopag if it is not active is  $\geq 81\%$  while there is at most a 9% chance of rejection if it is active.

Adverse events will be graded and categorized using CTCAE version 4.03 criteria. Assuming the trial reaches its maximum accrual goal of 31 eligible patients the likelihood of a particular type and/or grade of toxicity will be estimable using a 95% confidence interval that has a half-width of at most 18%. The likelihood of observing at least one such event is  $\geq 80\%$  even if the underlying risk is little as 5%.

Secondary goals of the trial include estimating the frequency of platelet transfusion independence, the effect of eltrombopag on hemoglobin, and neutrophils, the risk of clinically significant bleeding, clinical efficacy, and time to initiation of post-remission consolidation therapy.

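### Section 4.1 gives two eltrombopag start rules that do not match, and the wider one permits a first dose as late as the day-24 primary cut-off

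*Combined protocol and SAP*

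**What the plan says.** Day numbering is fixed in section 3.1, item 4, for the marrow that qualifies a patient: "range, day 14-17; day 1 refers to the first day of IC". Section 4.1 specifies cytarabine over 7 days and then, in consecutive sentences, gives two rules for the first dose:

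- Business-day rule: "eltrombopag will be administered within 5 business days from the date of day 14 (range, 14-17) bone marrow biopsy".
- Gap rule: "There will be a gap of at least one week (range, 7-9 days) between the last day of remission IC and initiation of eltrombopag".

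The study calendar in section 8.4 counts weeks from day 1 of IC. Its footnote a carries only the business-day rule: "The drug will be started within 5 business days from the date of day 14 bone marrow biopsy". The calendar puts the ECG marked with footnote m in week 3, and that footnote ties it to the day of the first dose. Adverse event monitoring also begins in week 3, and section 8.2 starts it on the day the study drug starts.

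The primary endpoint is a platelet count of at least 50,000/µL. Section 10.1.1 words the timing as "by day 24 of IC on eltrombopag therapy". Section 12 puts it this way: "The primary endpoint is the proportion of patients with early (by day 24 from the start of induction) platelet recovery". For the secondary platelet recovery times, section 10.2 says: "The initial time point for assessing different platelet recovery periods will be the first day of remission IC".

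**The concern.** The primary question is whether eltrombopag speeds platelet recovery, and the answer is read at a fixed day counted from the start of IC. The start rule therefore decides how much drug exposure can precede the endpoint. The two rules in section 4.1 give different latest start days, and the calendar implies a third window. A site following the business-day rule could give the first dose when little or none of the time to day 24 remains. Such a patient says little about the drug, whichever way the count falls. A site trying to follow both rules could find that an eligible patient has no permitted start day.

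A smaller, related point is that section 10.1.1 mentions being on eltrombopag and section 12 does not. No passage says how to score a patient who reaches 50,000/µL before the first dose.

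**Working it through.** **Design figures.** Section 12 continues if at least 8 of 12 patients recover and accepts if at least 21 of 31 do. The exact early-stopping probability is P(X₁ ≤ 7), with X₁ binomial(12, p): 0.562 at p = 0.60 and 0.073 at p = 0.80. Overall rejection is 1 − Σ P(X₁ = x)·P(X₂ ≥ 21 − x) over x = 8 to 12, with X₂ binomial(19, p): 0.806 at 0.60 and 0.089 at 0.80. The plan states 56%, 7%, 81% and 9%, so its figures reproduce to rounding. The issue is one of timing and wording, not of design arithmetic.

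**Gap rule.** Start day = last IC day + gap. With the last IC day equal to 7:

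- 7 + 7 = day 14 and 7 + 9 = day 16, so days 14–16.
- If the infusion ends on day 8, or if full days in between are counted: days 15–17.
- If both apply: days 16–18.

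**Business-day rule.** Five business days after a weekday marrow is 7 calendar days (holidays ignored), so the latest start is marrow day + 7. A weekend marrow brings this 1–2 days earlier. If the marrow day itself counts as the first business day, the latest start for a weekday marrow is day 18–20, 19–21, 20–22 or 21–23 for a day 14, 15, 16 or 17 marrow. The earliest start under this rule is the marrow day.

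**Both rules together.** The last column counts the days that satisfy both rules under the three gap conventions (14–16 / 15–17 / 16–18).

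| Marrow day | Latest start, business-day rule | Days from that start to day 24 | Start days satisfying both rules |
|---|---|---|---|
| 14 | 14 + 7 = 21 | 3 | 3 / 3 / 3 |
| 15 | 15 + 7 = 22 | 2 | 2 / 3 / 3 |
| 16 | 16 + 7 = 23 | 1 | 1 / 2 / 3 |
| 17 | 17 + 7 = 24 | 0 | 0 / 1 / 2 |

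The windows overlap for early starts. On the plain count, a day-17 marrow cannot comply, because even a same-day start is 17 − 7 = 10 days after IC. A start on day 21–24 is 14–17 days after IC, outside the 7–9 day range.

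**Time from first dose to day 24.** Under the gap rule it is 24 − 16 = 8 to 24 − 14 = 10 days (6–10 across counting conventions). At the latest starts under the business-day rule it is 0–3 days, where 0 means that the first dose falls on the cut-off day.

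**Calendar.** Week 3 is days 15–21. It leaves out day 14, which the gap rule allows, and days 22–24, which the business-day rule allows. It fits neither rule fully.

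**Endpoint wording.** Take a patient who reaches 50,000/µL before dosing, then starts the drug and still has at least 50,000/µL by day 24. That patient meets both wordings. The two part only if achieving the count is read as first crossing it on drug, or if the count falls, or if the patient is never dosed. Section 10.1.1 gives a historical range of 17–57 days for exceeding 50,000/µL (median 24). Recovery before a first dose on days 18–24 is therefore possible, but in that cohort none would have preceded a start on days 14–16.

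**The case against.** The best defence reads the text as a floor and a ceiling: at least one week after IC, and no later than 5 business days after the marrow, with 7–9 days merely describing usual practice. On that reading the rules do not conflict. It can also be said that the windows overlap for most marrow days, that days 21–24 are the extreme of one rule, and that the week-3 calendar entries suggest days 22–24 were not intended. The study schema and the calendar's medication bar, which were not visible in the text available, may state the start day.

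Much of this stands. The comparison of 0–3 with 8–10 days sets a worst case against a full range, and the documents give no frequency for late starts. But the floor-and-ceiling reading is precisely the one that permits a first dose on day 24. The calendar does not settle the matter, because it excludes day 14 as well.

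On the endpoint, a reader might infer that sections 10.1.1 and 12 define two different endpoints, or that recoveries before dosing inflate false acceptance. The documents support neither. Both sections count from the start of IC, and the phrase in 10.1.1 may simply describe the treated cohort. The 60% reference in section 12 is recovery by the same day without eltrombopag, so spontaneous early recovery is already part of it.

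**Conclusion.** The mismatch in the start rules is real and should be corrected. Its size is days 14–16 (day 18 at most) under one rule against a latest start of day 21–24 under the other, and 8–10 days against as little as 0–3 days from first dose to the primary cut-off. This assumes day 1 is the first day of IC, IC ends on day 7 or 8, the marrow is on a weekday, and no holidays intervene. The finding that a day-17 marrow has no compliant start holds only on the plain count with IC ending on day 7; other conventions leave 1–2 days.

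It would be tempting to conclude that late starts will be common, or that the trial cannot detect an effect. Nothing in the documents shows how often late starts would occur, so neither conclusion is supported. The difference in endpoint wording is minor and calls for alignment only. No view is taken on which start timing is clinically right.

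**What to change.** - Reconcile the two sentences in section 4.1, calendar footnote a and the week-3 calendar entries into one start window stated in IC days. The sponsor chooses the clinical rule, confirms that each permitted marrow day (14 to 17) has a start window, and checks the latest permitted start against the day-24 cut-off.
- Align section 10.1.1 with section 12 in one line: recovery to at least 50,000/µL by day 24, counted from the start of induction, which is the clock of the 60% reference.
- Alongside the primary result, report descriptively the days on drug by day 24 and the number of patients with platelets of at least 50,000/µL before the first dose. First-dose dates and blood counts suffice, and the counts are already collected: "CBC with differential will be monitored daily during hospital stay".

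The cost is a few wording edits and one small table. The sample size of 31, the 60% and 80% rates, and the 8/12 and 21/31 boundaries do not change.

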## 5.0 STUDY TREATMENTS

### 5.1 Supplier

Novartis will supply **PROMACTA®** (eltrombopag).

### 5.2 Dosage Form

Eltrombopag 200 mg once daily (two 100 mg tablets) has been selected as the starting dose for this study except for subjects of East Asian heritage who will start initially at 100 mg (one 100 mg tablet) daily. The maximum dose of study medication is 300 mg once daily (three 100 mg tablets) for all subjects except for patients of East Asian heritage who will be escalated to a maximum of 150 mg (one 100 mg and one 50 mg tablet) daily.

### 5.3. Pharmaceutical Presentation and Packaging

White, round, film-coated tablets without debossing are provided, containing eltrombopag olamine equivalent to 100 mg of eltrombopag free acid. Tablets are packaged in white HDPE bottles with white plastic, induction-seal, and child-resistant caps.

### 5.4 Storage and Handling

The recommended storage condition is stated on the product label and, where required, the label also includes the expiry date.

### 5.5 Receipt of Study Drug

The Investigator or designee is responsible for taking an inventory of each shipment of **PROMACTA®** (eltrombopag) received, and comparing it with the accompanying study drug

accountability form. The Investigator will verify the accuracy of the information on the form, sign and date it, retain a copy in the study file, and return a copy to Novartis or its representative. The bottle numbers, if present, must be recorded when **PROMACTA®** (eltrombopag) is received and dispensed.

## **5.6 Storage**

At the study site, the investigational study drug will be stored in a locked, safe area to prevent unauthorized access. **PROMACTA®** (eltrombopag) should be stored at room temperature away from direct sunlight and protected from excessive heat and cold.

## **5.7 Unused Study Drug Supplies**

Novartis will instruct the Investigator on the return or destruction of unused **PROMACTA®** (eltrombopag). If any eltrombopag is lost or damaged, its disposition should be documented in the source documents. **PROMACTA®** (eltrombopag) study supplies will be retained at the clinical site pending instructions for disposition by Novartis. Participants will be instructed to return empty bottles and unused capsules.

